Study Protocol and Statistical Analysis Plan

Study Title:
TeamTRACS Pilot (CTSI)

ClinicalTrials.gov ID (NCT number):
NCT05370157

Document Date:
March 14, 2024

Study Overview

This research study is a cluster-randomized controlled effectiveness-implementation hybrid trial of TeamTRACS. The trial will take place in 6 rural Child Advocacy Centers (CACs) in the southern United States. It will use mixed methods (quantitative and qualitative) to evaluate the effects of TeamTRACS and assess the acceptability, appropriateness, and feasibility of self-guided implementation via pre/post surveys and qualitative interviews.

The primary aims of this pilot trial are to test the effects of TeamTRACS on knowledge, skill use, and team functioning in addition to evaluating the acceptability, appropriateness, and feasibility of self-guided implementation. Six rural CACs will be randomized to TeamTRACS ($n = 4$ CACs) or a waitlist comparison ($n = 2$ CACs). Participants will be team members at participating CACs (estimated $N = 25$ per CAC; total $N = 150$). We expect team members to change during the study period and will include only current team members at each timepoint. We will evaluate the effects of TeamTRACS on learning (i.e., knowledge), transfer (i.e., skill use), and results (i.e., team functioning). Knowledge, skill use, and team functioning will be assessed at baseline and 3 months with online surveys and qualitative interviews of team members. We will also assess hypothesized long-term outcomes (i.e., team performance, workforce outcomes). Individuals involved in implementation in the 4 CACs randomized to TeamTRACS will participate in semi-structured key informant interviews during the implementation process. They will rate the acceptability, appropriateness, and feasibility of self-guided implementation at the beginning, middle, and end of the study, and we will track completion of implementation activities in each CAC.

Background

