This research study will test the effectiveness of TeamTRACS in a cluster-randomized trial in 6 rural Child Advocacy Centers. We will also partner with the National Child Advocacy Center (NCAC) to refine our implementation strategies. Rural teams serving high-need/low-resource areas may find it challenging to implement new practices. This study will use a self-guided implementation approach that requires few resources and builds local capacity for change. We will assess the acceptability, appropriateness, and feasibility of self-guided implementation in participating CACs. Self-guided implementation will allow the training to be rapidly scaled up and disseminated to CACs nationwide. Improving teamwork in CACs has the potential to positively impact service quality and outcomes for hundreds of thousands of children served by CACs.

Procedures

Randomization

CACs will be randomized to TeamTRACS ($n = 4$) or a waitlist comparison ($n = 2$) using an online randomization tool. We may stratify CACs based on team size if there is significant variability across the 6 CACs. CACs randomized to TeamTRACS will receive the intervention described below after completing the baseline survey. CACs randomized to the waitlist will receive the intervention after completing the follow-up survey.

Team Training Intervention

TeamTRACS (**T**eam **T**raining in **R**oles, **A**wareness, **C**ommunication, and **S**upport), is a team training intervention that is adapted from TeamSTEPPS (Team Strategies and Tools to Enhance Performance and Patient Safety), which is a widely used evidence-based team training approach developed by the Agency for Healthcare Research and Quality. TeamTRACS was developed via a systematic and participatory adaptation process (see McGuier et al., 2023).

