In the 4 CACs randomized to TeamTRACS, key informants (leadership and team members involved in the implementation process) will be invited to participate in qualitative interviews. Semi-structured interviews will be conducted approximately once a month during the implementation process to assess change over time. Questions will assess perceptions of and experiences with self-guided implementation, as well as progress through implementation phases and steps (see “Implementation Interview Guide”). Interviews will take 30-60 minutes. Key informants will also rate the acceptability, appropriateness, and feasibility of self-guided implementation at the beginning, middle, and end of the study.

Document Collection

CAC staff at the 4 CACs randomized to TeamTRACS will be asked to share documents created during the implementation process, including completed worksheets, action plans for training, team goals, and revised policies or protocols. The research team will review documents to assess fidelity to the implementation guide and completion of implementation activities. At all 6 CACs, staff will be asked to report team members’ attendance at case review meetings and any changes in team members (e.g., turnover, addition of new members).

Statistical Analysis Plan

Preparatory Analyses

We will calculate survey response rates, look for patterns of missing data, and examine descriptive statistics for all measures.

Analyses of Effectiveness Outcomes

We will test changes in knowledge, skill use, and team functioning from baseline to 3-month follow-up using linear mixed models to account for repeated measures and clustering within CACs. We will also explore changes in team performance and team member outcomes. Our primary analyses are intent-to-treat analyses including all participants in each condition. We will also conduct ‘per protocol’ analyses testing for changes in knowledge and skill use by training attendance. This pilot study is adequately powered to detect changes in individual outcomes (e.g., knowledge of teamwork skills), but underpowered for team-level outcomes. Accordingly, after aggregating measures of team functioning and performance to the team level (assuming sufficient within-team agreement), we will plot data to visually examine team-level results.

Analyses of Implementation Outcomes

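### The claim of adequate power for individual outcomes has no stated inputs or contrast, and is unsupported for the randomised comparison of 4 CACs with 2

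*Combined protocol and SAP*

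**What the plan says.** The Study Overview makes it a primary aim to "test the effects of TeamTRACS on knowledge, skill use, and team functioning", and the Background section says: "This research study will test the effectiveness of TeamTRACS in a cluster-randomized trial in 6 rural Child Advocacy Centers". The allocation is 4 CACs to TeamTRACS and 2 to the waitlist, with about 25 members expected at each and 150 in all. Membership is open: "We expect team members to change during the study period and will include only current team members at each timepoint".

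The SAP, under Analyses of Effectiveness Outcomes, describes the test in these words: "We will test changes in knowledge, skill use, and team functioning from baseline to 3-month follow-up". The method for that test is given as "using linear mixed models to account for repeated measures and clustering within CACs". On the population it says: "Our primary analyses are intent-to-treat analyses including all participants in each condition". The only power statement in the documents is in the same section: "This pilot study is adequately powered to detect changes in individual outcomes (e.g., knowledge of teamwork skills), but underpowered for team-level outcomes". No effect size, ICC, correlation over time, alpha, target power or expected response rate accompanies it. The SAP does not name an arm-by-time term, list the random effects or give a degrees-of-freedom method.

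**The concern.** Measuring knowledge on individuals does not change the unit of randomisation. The SAP concedes low power for team-level outcomes and exempts individual ones, yet the same six CACs limit the between-arm comparison of both. It is also unclear what the claim refers to. Change could mean movement within an arm, or the difference in change between arms, and only the second is protected by randomisation.

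Two readings of the results are at stake. A reader who trusts the sentence would give a non-significant between-arm result more weight than six CACs can usually bear. And if the model omits CAC-specific shifts over time, a significant result may not carry a 5% error rate.

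**Working it through.** **No stated figure to reproduce.** The documents give no power, detectable effect or sample-size derivation.

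**Inputs from the Study Overview.** 4 and 2 CACs; m = 25 members per CAC.

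**Assumed inputs.** Two-sided 5%; ICC 0.01, 0.05, 0.10; CAC autocorrelation (a CAC's own level at baseline against 3 months) 0.8, 0.9, 1.0; within-person correlation r 0.5, 0.6, 0.7, 0.8. That makes 36 combinations. Response is 100%, or 70% (m = 17.5). Effects are in SDs of the outcome.

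**Formulas.**
- Variance of a CAC's mean change: V = 2·ICC·(1 − autocorrelation) + 2·(1 − ICC)·(1 − r)/m.
- Standard error of the between-arm difference: √[V·(1/4 + 1/2)].
- Power: noncentral t with 6 − 2 = 4 df (critical value 2.776).
- Baseline-adjusted version: replace V by v − c²/v, with v = ICC + (1 − ICC)/m and c = autocorrelation·ICC + (1 − ICC)·r/m. The slope is taken as known, which is slightly generous.

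**One cell in full.** Take ICC 0.05, autocorrelation 0.8, r 0.5, m = 25. V = 2(0.05)(0.2) + 2(0.95)(0.5)/25 = 0.020 + 0.038 = 0.058. The standard error is √(0.058 × 0.75) = 0.209. For 0.5 SD the noncentrality is 0.5/0.209 = 2.40 and power is 45%. For 0.8 SD power is 81%. The difference detectable with 80% power is 0.78 SD.

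**Cells out of 36 that reach 80%** (power rounded to a whole percent):

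| True difference in change | Change score, m = 25 | Baseline-adjusted, m = 25 | Change score, m = 17.5 | Baseline-adjusted, m = 17.5 |
|---|---|---|---|---|
| 0.5 SD | 8 | 11 | 3 | 4 |
| 0.6 SD | 16 | 24 | 9 | 11 |
| 0.7 SD | 27 | 30 | 17 | 25 |
| 0.8 SD | 33 | 35 | 29 | 32 |
| 1.0 SD | 36 | 36 | 36 | 36 |

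At 0.5 SD with change scores and full response, power runs from 36% to 94%. The cells that reach 80% all have r of 0.7 or 0.8. At autocorrelation 0.8 and r 0.5-0.7, the detectable difference is 0.54-0.68 SD at ICC 0.01, 0.67-0.78 at 0.05 and 0.81-0.90 at 0.10.

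**Turnover.** A high r helps only for people surveyed twice. In the limiting case where nobody is (r = 0), power for 0.5 SD is 27-38% over the same ICCs and autocorrelations with change scores and m = 25.

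**Within-arm change.** For the 4 TeamTRACS CACs alone, the variance is V/4 with 3 df. A change of 0.5 SD reaches 80% power in 31 of 36 cells at full response.

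**Effect of the random-effects choice.** In paired data, CAC and person intercepts cancel from each person's change. A model with only those terms therefore treats the 100 and 50 changes as independent. In three simulated paired data sets it gave the same arm-by-time estimate as a person-level test of changes, with a standard error within 1%. In the cell above, that test uses a variance of about (0.95 + 0.02)(1/100 + 1/50) = 0.0291, while the true variance is 0.058 × 0.75 = 0.0435. The two-sided error is then about P(|Z| > 1.96/√(0.0435/0.0291)) = P(|Z| > 1.60) = 11%. Simulating the person-level test over all ICCs and r values gives type I error of about 6-29% at autocorrelation 0.8, 6-19% at 0.9 and 5% at 1.0. With no CAC-level variance at all, the same model would show 82% power for 0.5 SD at r 0.5 and 96% at r 0.7.

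**The case against.** The strongest objection is that 0.5 SD appears nowhere in the documents. The conclusion turns on it: with change scores and full response, most cells fall short at 0.5 SD, but 27 of 36 reach 80% at 0.7 SD and 33 at 0.8 SD. A training programme may well move knowledge that far. This stands. A reader might infer from the 0.5 SD figures that the power claim is false; the documents do not support that, because they name no effect against which to judge it.

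Second, the SAP speaks of detecting changes, and for within-arm change the sentence is mostly true. That also stands, but such a change is uncontrolled, so the objection shows why the contrast must be named.

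Third, the SAP already commits to mixed models that allow for clustering. It does. What is open is whether clustering includes CAC-by-time variation, and the error rate depends on that. A reader might infer that the planned analysis will be anti-conservative. The text does not fix the model, so it only allows that outcome.

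Fourth, 4 df describes a comparison of CAC mean changes. A fitted mixed model need not return exactly 4, especially if the CAC-by-time variance is estimated at zero. The power figures are therefore a guide. The cell counts depend on the grid and are not evidence about this trial's true ICC.

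Finally, this is a pilot. But testing effects is a stated aim, and the plan chose to assert adequate power.

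**Conclusion.** The concern holds as a gap in support and specification; no calculation in the plan is shown to be wrong. It is certain from the text that the power sentence has no inputs and no contrast, and that the random effects and degrees-of-freedom method are unstated. The size rests on the assumed ICC, autocorrelation, within-person correlation and response. Under these, the randomised comparison reliably detects only fairly large differences, of roughly 0.7-0.8 SD or more at full response. Turnover or 70% response pushes this higher. The inflated type I error arises only if CAC-by-time variation exists and the model leaves it out. The point should be fixed, because it changes what either a null or a significant between-arm result can be taken to mean.

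**What to change.** Remove the assertion of adequate power. Alternatively, replace it with the between-arm difference in change detectable at 80% power, with the sponsor's own ICC, CAC and within-person correlations, alpha, expected response and turnover written beside it.

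Add to Analyses of Effectiveness Outcomes: the primary contrast for individual outcomes is the arm-by-time effect; the mixed model includes CAC-by-time variation and uses a named small-sample degrees-of-freedom method; between-arm estimates are reported with 95% confidence intervals; non-significance will not be read as absence of effect. Any within-arm change should be labelled as uncontrolled.

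This changes SAP wording and model specification only, and needs no extra CACs. The cost is wider confidence intervals and a less favourable power statement.

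### Team functioning is assigned both a mixed-model test and, as underpowered, a team-level plot; the plan does not say which carries the conclusion, and both rest on the same six CACs

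*Combined protocol and SAP*

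**What the plan says.** The Study Overview states: "The primary aims of this pilot trial are to test the effects of TeamTRACS on knowledge, skill use, and team functioning". It goes on to add acceptability, appropriateness and feasibility of self-guided implementation. Team functioning is therefore one of three effectiveness outcomes within a wider set of primary aims. Six CACs are randomised, four to TeamTRACS and two to waitlist, with about 25 members expected in each.

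Under Analyses of Effectiveness Outcomes, one paragraph deals with team functioning twice:

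- As a tested outcome: "We will test changes in knowledge, skill use, and team functioning from baseline to 3-month follow-up using linear mixed models". The models are to allow for repeated measures and clustering by CAC. No random-effects structure, arm-by-time contrast or degrees-of-freedom method is given.
- As a displayed outcome: "This pilot study is adequately powered to detect changes in individual outcomes (e.g., knowledge of teamwork skills), but underpowered for team-level outcomes". As a consequence of that statement, team functioning and performance are to be aggregated to team level if within-team agreement suffices, and then "we will plot data to visually examine team-level results". No agreement index or threshold is named, and nothing is said about what happens if agreement is insufficient.

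**The concern.** The paragraph implies that analysis of individual ratings has adequate power while analysis of team values does not. For a randomised comparison of arms that contrast is not available. The CAC is the unit of allocation, so uncertainty about the arm difference depends on how much CACs vary, however many members are surveyed in each.

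Two things are at stake. First, the plan leaves open whether the conclusion on team functioning comes from a p-value on ratings or from a plot. Second, if the mixed model omits CAC-level variation in change, its p-value could be far too small. That would matter for an intervention which the Background intends for nationwide dissemination.

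**Working it through.** **The plan's own figures.** 6 × 25 = 150 members, or 4 × 25 = 100 against 2 × 25 = 50. This agrees with the stated total. The power statement is in words only, with no effect size, ICC, SD or power, so it cannot be reproduced.

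**Same information at both levels.** With equal CAC sizes, the arm effect from a random-intercept mixed model equals the difference in CAC means; in simulated data the largest discrepancy was about 2 × 10⁻¹⁵. Individual ratings leave the estimate unchanged. What can differ is the standard error attached to it.

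**Assumed inputs (none in the documents).** Outcome SD 1; ICC at one timepoint ρ; cluster autocorrelation c = 0.8-0.9; within-person correlation r = 0.5-0.7; complete pairs, 25 per CAC.

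**Formulas for change from baseline to 3 months.**

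- Between-CAC variance of change: B = 2ρ(1 − c)
- Within-CAC variance of change: W = 2(1 − ρ)(1 − r)
- True SE of the arm difference: √[0.75 × (B + W/25)], where 0.75 = 1/4 + 1/2
- SE implied by person and CAC intercepts only: about √[(B + W) × (1/100 + 1/50)]. Both intercepts cancel from change scores, so CAC-level variation in change is treated as independent between members.
- Ratio of the two SEs: √D, where D = 1 + 24 × B/(B + W)

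**Worked case, ρ = 0.2, c = 0.8, r = 0.5.**

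- B = 2 × 0.2 × 0.2 = 0.08 and W = 2 × 0.8 × 0.5 = 0.80.
- True SE = √[0.75 × (0.08 + 0.032)] = √0.084 = 0.290.
- Implied SE = √(0.88 × 0.03) = 0.162.
- D = 1 + 24 × 0.08/0.88 = 3.18, so the ratio is 1.78. A nominal 1.96 is really 1.96/1.78 = 1.10 standard errors, giving a two-sided error of about 27%.
- On 4 df the 95% half-width is 2.776 × 0.290 = 0.80 SD.

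**Range over the assumptions** (type I error from 40,000 simulated null trials per setting; power from the non-central t on 4 df):

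| | ICC 0.05-0.10 | ICC 0.2-0.3 |
|---|---|---|
| Type I error, person and CAC intercepts only | about 8-23% | about 18-45% |
| Type I error, CAC-mean t-test on 4 df | about 5% | about 5% |
| 95% CI half-width, 4 df | 0.44-0.66 SD | 0.59-0.93 SD |
| Power for 0.5 SD, 4 df | 36-67% | 21-44% |

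At ICC 0.2-0.3, B/(B + W) is 0.048-0.22 and D is 2.1-6.3, so 150 members carry the information on change of about 150/6.3 = 24 to 150/2.1 = 70 independent people.

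**A milder set-up.** At a single timepoint with ICC 0.10, a random-intercept model with a Wald z test rejected in 9% of 300 null datasets, against 3% for the CAC-level t-test. With so few runs these rates are approximate, but the direction agrees.

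**The case against.** A reader might infer that the paragraph contradicts itself, with team functioning both tested and only plotted. The text does not support that. It never says only plotted, and a member-level model beside a descriptive team-level display is a coherent pair. A reader might also infer that the plan yields no effect estimate, or that the form of reporting will be picked after seeing the data. Neither follows: both analyses are stated as commitments, the mixed model would give an estimate and interval, and the agreement condition governs aggregation, not whether the model is fitted. These objections stand.

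It can fairly be added that the high error rates belong to one model, which the SAP permits but does not specify. A CAC-by-time effect with small-sample degrees of freedom would also satisfy the wording. That stands too, and it is why the figures are conditional. Every correlation is assumed, and complete pairs are an idealisation, since the Study Overview expects members to come and go. By the formulas above, a lower effective r reduces the inflation but widens the correct interval.

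It is tempting to argue that good within-team agreement is just when individual ratings add least. That equates agreement with ICC; members can agree closely while teams hardly differ. The point does not rest on it.

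Finally, six clusters limit knowledge and skill use equally. That is correct and widens the issue. Team functioning stands out because the plan itself gives low power as the reason for plotting it, while also naming it for a test.

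**Conclusion.** The concern holds as a gap in specification. The SAP does not say which analysis carries the conclusion on team functioning, and its implied distinction between adequately powered individual analysis and underpowered team analysis fails for the between-arm comparison, because both use the same 4 v 2 CACs.

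The possible harm is a type I error of about 18-45% at ICC 0.2-0.3, or about 8-23% at ICC 0.05-0.10, if the model has person and CAC intercepts only. These figures rest wholly on the assumed correlations and on that model; they do not correct any stated figure. The plan speaks of testing changes without naming an arm contrast. A purely within-arm change would have different precision, but it would not be the randomised comparison.

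The six-cluster limit does not depend on those assumptions. For a pilot the gap is worth closing because doing so is nearly free and alters what may be concluded about a primary-aim outcome.

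**What to change.** Amend Analyses of Effectiveness Outcomes to state that:

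1. The inferential result for team functioning (and, as exploratory, team performance) is the TeamTRACS minus waitlist difference in CAC-mean change with a 95% CI on 4 df, or an equivalent mixed model with a CAC-by-time effect and small-sample degrees of freedom.
2. This result is labelled underpowered, and no effect will be claimed from an individual-level model without those features.
3. Plots of all six CACs accompany the estimate, with a named agreement index reported alongside.

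A test on 4 df need not be excluded; barring every test would conflict with the stated aim of testing effects. The same six-cluster limit should be acknowledged for knowledge and skill use.

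The change needs SAP wording only and no new data. Its price is a visibly wide interval, about 0.6-0.9 SD either side under the ICC 0.2-0.3 assumptions, and less chance of a significant result. Both fit the plan's own admission of low team-level power.

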TeamTRACS targets knowledge, skills, and attitudes related to team member roles, shared awareness, communication, mutual support, and goal-setting. TeamTRACS is structured, easy to use, flexible in length and intensity, and requires few resources. It incorporates didactic instruction, discussion, and interactive activities and can be delivered virtually or in-person. Presentation slides, detailed instructor guides, and worksheets were created for each module (see “TeamTRACS Instructor Guide”). Team members are encouraged to identify specific goals for their team and make plans to use specific strategies from the training. The training will be delivered in a single session and be at least 4 hours. Teams will determine the length and delivery method (e.g., in-person vs. virtual) as part of the implementation process. The training workshop will be facilitated by an experienced team trainer from NCAC; this approach is responsive to pilot data favoring use of an external facilitator and is sustainable given available resources.

All team members at each CAC will be invited to participate in the training. Prior to the start of the training, the PI will review a brief consent script and provide an opportunity for questions. A copy of the consent script will be provided to all team members. We will record team members’ attendance at the training.

Baseline and Follow-up Surveys

Team members will complete online surveys (<30 minutes) before training and 3 months after training via REDCap, a secure online database. The surveys will assess knowledge and use of teamwork skills, team functioning, team performance, and team member work outcomes (see “Team Member Survey”). Team members will be sent an email with information about the study and a link to review the online consent form.

Key Informant Interviews

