We will use rapid analysis to code qualitative key informant interviews using an a priori coding scheme focused on barriers, facilitators, and suggestions for change. We will assess the proportion of implementation activities completed in each CAC and examine descriptive

statistics for acceptability, appropriateness, and feasibility ratings. Mean ratings >4 on the 1-5 scale will indicate that TeamTRACS is acceptable, appropriate, and feasible.

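### The plan's only numeric success rule gives its verdict on TeamTRACS, while the ratings it describes are of self-guided implementation

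*Combined protocol and SAP*

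**What the plan says.** The SAP, under Analyses of Implementation Outcomes, plans descriptive statistics for the acceptability, appropriateness and feasibility ratings, without naming there what is rated. It then sets the criterion: "Mean ratings >4 on the 1-5 scale will indicate that TeamTRACS is acceptable, appropriate, and feasible".

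Study Overview says that the trial will "evaluate the effects of TeamTRACS and assess the acceptability, appropriateness, and feasibility of self-guided implementation via pre/post surveys and qualitative interviews". Its statement of primary aims makes the same pairing. Of the people involved in implementation at the four TeamTRACS centers it says: "They will rate the acceptability, appropriateness, and feasibility of self-guided implementation at the beginning, middle, and end of the study". Background adds: "We will assess the acceptability, appropriateness, and feasibility of self-guided implementation in participating CACs". Key Informant Interviews repeats the rating schedule, with key informants as raters and self-guided implementation as the object.

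TeamTRACS is defined separately. Under Team Training Intervention it "is a team training intervention that is adapted from TeamSTEPPS".

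**The concern.** The sentence that turns ratings into a verdict has a different subject from every sentence that says what those ratings are about. An analyst would know which data to use, because only one set of such ratings is described. The difficulty is the conclusion: a favorable mean for the implementation approach would, by the rule's own words, count as evidence that the training is acceptable, appropriate and feasible.

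Two things are at stake. First, the acceptability, appropriateness and feasibility of self-guided implementation are part of the stated primary aims, and the rule as worded gives them no benchmark. Background rests nationwide scale-up on self-guided implementation, so that is where a benchmark is wanted. Second, Background reports that an earlier pilot in one rural center found ratings above 4 on a 1-5 scale for TeamTRACS itself. The SAP sentence uses the same constructs, scale, cut-off and object, so a pass could be read as replicating that result when the ratings described here concern something else.

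**Working it through.** No arithmetic applies. The cut-off of 4 is chosen, not derived, and the question is what it judges. The check sets the passages side by side.

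**1. What is to be assessed on these constructs in this trial.**

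| Place | Object named | Describes ratings? |
|---|---|---|
| Study Overview, opening paragraph | Self-guided implementation | No |
| Study Overview, primary aims | Self-guided implementation | No |
| Study Overview, rating schedule | Self-guided implementation | Yes |
| Background, last paragraph | Self-guided implementation | No |
| Key Informant Interviews | Self-guided implementation | Yes |
| **Total** | **5 of 5 self-guided implementation; 0 of 5 the training** | **2 of 5** |

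**2. Whether the two terms mean the same thing.** They do not. The opening paragraph and the primary aims both set the effects of TeamTRACS beside these constructs for self-guided implementation, as two tasks. Background describes the latter as a way of working: "This study will use a self-guided implementation approach that requires few resources and builds local capacity for change". The training, by contrast, is delivered from outside: "The training workshop will be facilitated by an experienced team trainer from NCAC". A well-received external workshop could follow a burdensome self-guided process, or the reverse, so a rating of one does not establish the other.

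**3. Whether another described source rates the training.** The content listed under Baseline and Follow-up Surveys is teamwork knowledge and skill use, team functioning, team performance and work outcomes. No acceptability, appropriateness or feasibility rating is listed. The pilot result in Background concerns the training but is past data.

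**4. Who rates.** The only raters described are key informants: leadership and team members involved in implementation. The training has a wider audience: "All team members at each CAC will be invited to participate in the training". The number of key informants is not given, so the overlap cannot be sized.

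**5. Whether any other numeric success rule exists.** None does. The effectiveness analyses give no alpha, effect size, power value or threshold, and the proportion of implementation activities completed has no cut-off. The pilot figure in Background is a result, not a rule.

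So the plan has one numeric rule, its verdict is on TeamTRACS, and no rating of TeamTRACS is described for this trial.

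**The case against.** The strongest reply is that the direction of the error is not certain. Because the criterion matches the pilot result so closely, the SAP sentence may be deliberate and refer to a rating of the training that the procedures do not describe. The team member survey and the implementation interview guide are cited but not supplied, and the survey summary is a single sentence, which is weak evidence of absence. This stands: a reader might infer that the trial certainly does not rate the training, and the documents do not support that. Loose wording in the SAP is the likelier explanation, but an undescribed rating cannot be excluded.

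A reader might also infer that key informants are certainly the only raters. The opening paragraph of Study Overview mentions pre/post surveys in the same sentence as these constructs, and on one grammatical reading the surveys contribute to assessing them. The supportable statement is that key informants are the only raters described.

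It can also be said that TeamTRACS is shorthand for TeamTRACS adopted by self-guided implementation, since the rule sits among the implementation outcomes. That is possible. But the documents otherwise keep the terms apart, and this is the sentence that states the conclusion. If it is shorthand, a few words settle it.

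Finally, no data, model or calculation changes, and the benchmark is descriptive. That is true and limits the weight of the point, but it does not make the sentence consistent with the aim.

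**Conclusion.** The concern holds as an inconsistency of object. All five prospective statements name self-guided implementation; the one numeric rule names TeamTRACS. Followed as written, the rule draws a conclusion that the described ratings do not support and leaves part of a primary aim without a benchmark. It should be corrected, although it is one sentence about a descriptive criterion in a pilot.

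The effect on the pass or fail result cannot be computed from the documents. It is nil if the training and the implementation approach would both fall on the same side of 4. A reader might infer that the verdict would be reversed, or that a misattributed claim will be published; the documents show neither. What they show is that the rule licenses the misattribution.

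The conclusion assumes that the procedures describe all ratings of these constructs. If an instrument not supplied also rates the training, the defect is instead an undescribed measure, and the aim for self-guided implementation still lacks its own criterion.

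Ratings are taken at three points, and the SAP says neither which decides nor how ratings are pooled. That is a separate matter of optional pre-specification and adds nothing to this error.

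**What to change.** In the criterion sentence of the SAP, replace TeamTRACS as the subject with self-guided implementation of TeamTRACS, keeping the cut-off and scale. State that no conclusion about the training will be drawn from these ratings.

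If the survey or interview guide does rate the training, add to the procedures who gives that rating and when, and state a separate criterion for it in the SAP.

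If the study team wishes, one further sentence can name the deciding occasion and say whether the mean is pooled over raters or averaged over the four centers. That is their choice.

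The correction costs a few words in one sentence, with no new data and no change to the threshold or the analysis. The downside is that the trial then claims nothing about the acceptability, appropriateness or feasibility of the training unless the training is rated.
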